5.2.4 Safety variables

Any adverse event (AE) or serious adverse event (SAE) as described below.

Table 4. Demographics and perioperative data to be collected
Patient data
Age
ASA class
Concomitant therapy
Surgery type
Last menstruation date
TNM stage: size T1-T4; pathological node status N0, N1-3, N>3
Tumor type
Histological tumor grade (grade 1-3)
Receptors (E+/P+; E+/P-; E-/P+; E-/P-; HER2+)
Ki67>35%
Extracapsular tumor spreading
Peroperative data
Anesthesia duration (min)
Mean expiratory fraction in group sevoflurane (Exp%)
Total amount of propofol in group propofol (mg)
Mean BIS value
Total amount of fentanyl (mg)
Mean core temperature (°C)
Administration of b-blockers or COX-inhibitors (yes/no)
Administration of PONV prophylaxis (yes/no)
Blood transfusion (number of units)
Postoperative data
Total amount of morphin in PACU (mg)
Total amount of morphin on the ward (mg)
Administration of b-blockers or COX-inhibitors (yes/no)
Administration of PONV prophylaxis (yes/no)
Blood transfusion (number of units)

6. STUDY DESIGN

6.1 General Design

We will conduct a prospective, randomized, double blinded, controlled study over a period of 52 months. We will consider adult female patients undergoing surgery for primary breast cancer. Expecting a dropout rate of 10% over time, we will recruit a total of 232 patients (i.e. 116 in each study group).

Patients will be screened for eligibility according to the inclusion and exclusion criteria on the day prior to surgery. Written informed consent will be subsequently obtained. A pregnancy test will be performed for all included patients.

On the day of operation, the patients will be premedicated with midazolam *per os* (3.75mg to 7.5mg). Randomization will be performed according to a computer-generated anesthesia-assignment (www.randomizer.at) once the patient will be installed for induction of anesthesia. By this means, concealment of random allocation will be ensured.

After preoxygenation, induction of anesthesia will be administrated in both groups similarly, using fentanyl 2-3mcg/kg, Pentothal 4-6 mg/kg and rocuronium 0.6mg/kg intravenously. Maintenance of anesthesia will be conducted following the assignment group:

1) in “Group Sevo”, anesthesia will be maintained with sevoflurane in 80% oxygen, adjusted to keep an adequate depth of anesthesia (minimal alveolar concentration (MAC) between 0.8 and 1.2), attested by bispectral (BIS) index values between 40 and 60.

2) in “Group Propofol” anesthesia will be maintained with a target-controlled infusion (TCI) device providing an intravenous propofol dose adjusted to keep an adequate depth of anesthesia (TCI values: start after induction with 2.0mcg/ml, then ranging from 3.0mcg/ml to 5.0mcg/ml), attested by BIS index values between 40 and 60.

Patients will be ventilated with 80% oxygen in air.

Patients requiring a rapid sequence induction will receive rocuronium 0.9mg/kg instead of 0.6mg/kg. Per- and postoperative analgesia will be provided following a standardized protocol: fentanyl 2mcg/kg (total dose ranging from 5-10mcg/kg) will be used during surgery; surgical wound infiltration with local anesthetics will not be allowed; morphine intravenous 0.02-0.04mg/kg for a VAS <4 will be used in the PACU, whilst subcutaneous morphine (0.1-0.2mg/kg will be prescribed as second line analgesic once patients will be discharged from PACU. Basic postoperative analgesia will be provided using paracetamol and non-steroidal anti-inflammatory drugs. Postoperative nausea and vomiting (PONV) prophylaxis will be prescribed following a strict protocol (no glucocorticoids).

6.2 Primary Study Endpoint: blood CTC levels

The primary endpoint, blood CTC levels, will be assessed at 4 pre-defined time points using the CellSearch® approach: two 7.5ml samples of blood will be collected pre-operatively (visit 2, before induction of anesthesia), at the end of surgery (visit 3, before extubation) and two times postoperatively (visit 4, 48h postoperative, and visit 5, 72h after surgery, before hospital discharge). The number of CTC per 7.5ml of peripheral blood will be determined by the CellSearch® system within 96 hours of blood collection. The analysis will account for the effect of repeated measurements over time (within-subject factor) and the effect of anesthesia regimen (between-subject factor) as described under section 12.

The CellSearch® approach

The CellSearch® assay contains a ferro fluid-based capture reagent and immunofluorescent reagents. The ferrofluid reagent consists of particles with a magnetic core surrounded by a polymeric layer coated with antibodies targeting the epithelial cell adhesion molecule (EpCAM) antigen for capturing CTC. After immunomagnetic capture and enrichment, fluorescent reagents (anti-CK-phycoerythrin, DAPI, and anti-CD45-allophycocyanin) are added for identification and enumeration of CTC. (www.veridex.com)

6.3 Secondary Endpoints

6.3.1 Anesthesia, NK cells and tumor spreading

The assessment of NK cells (mean number and activity) will be performed at 4 pre-definite time points, concomitant to CTC determination. The analysis will account for the effect of repeated measurements over time (within-subject factor) and the effect of anesthesia regimen (between-subject factor) as described under section 12.

6.3.2 CTC positivity and extracapsular tumor spreading

Pathology reports from patients undergoing surgery with axillary lymph node dissection will be reviewed for extracapsular tumor spread with the aim to establish a correlation between CTC positivity and ECS.

6.3.3 Safety Endpoints

Adverse events (AE) or serious adverse events (SAE) will be actively sought and reported. For comprehensive description of AE/SAE, see paragraph 10 below.

6.4 Study procedures (fig.1)

6.4.1 Visit 1 (preoperative day)

- Standard pre-anesthesia visit: medical history, physical examination, demographics (as listed in Table 1)

- Check for eligibility according to the inclusion and exclusion criteria
- Information of patient and written informed consent
- Pregnancy test: if not pregnant, the patient will qualify for the study
- Concomitant therapy* will be administered
- Potential confounders will be documented

6.4.2 Visit 2 (day of surgery – before induction of general anesthesia)

- Vital signs will be recorded, concomitant therapy* will be administered
- Patient randomization to “Group Sevo” (experimental) or to “Group Propofol” (control)
- 2x7.5ml + 2x8ml of blood will be collected and sent for CTC/NK cells assessment (1° variable and 2° variable A)

6.4.3 Visit 3 (day of surgery – end of surgery, before extubation)

- Maintenance of anesthesia following the assignment group (sevoflurane or propofol)
- Vital signs will be recorded, concomitant therapy* will be administered
- 2x7.5ml + 2x8ml of blood will be collected and sent for CTC/NK cells assessment (1° variable and 2° variable A)
- Histopathological findings (2° variable B): data related to this endpoint will be collected after completion of the study.
- Perioperative data collection as listed in Table 3
- AE or SAE will be recorded

6.4.4 Visit 4 and 5 (48h and 72h postoperative)

- Vital signs will be recorded, concomitant therapy* will be administered
- 2x7.5ml + 2x8ml of blood will be collected and sent for CTC/NK cells assessment (1° variable and 2° variable A), concomitant to routine postoperative laboratory tests
- Perioperative data collection as listed in Table 3
- AE or SAE will be recorded

* For medications susceptible to interfere with outcome measure, see paragraph 8.5 below

[figure not shown]

Fig.1 Trial profile. Each visit is highlighted in a different color.

7. SUBJECT SELECTION AND WITHDRAWAL

Patients undergoing surgery for breast cancer will be enrolled at the University Hospital of Zürich (USZ) and at Klinik Hirslanden Zurich. The Department of Gynecology and Breast Cancer Center of the USZ perform about 150-200 operations per year for breast cancer. Based on USZ last year records, we expect to enroll 5-10 patients per month; slightly lower enrollment rates are expected at Klinik Hirslanden, (3-8 patients/month).

Meetings with the anesthesia team USZ and the investigators of Klinik Hirslanden will be organized periodical at least all 6 month, to identify at an early stage potential enrolment or organizational issues. These meetings are also expected to act as a positive feedback and motivational tool.

Patients fulfilling all of the following inclusion criteria will be enrolled in the study:

7.1 Inclusion Criteria

- 18 to 85 years old
- Female patients
- Primary breast cancer without known remote extension
- Scheduled for tumor resection or mastectomy, +/- axillary node dissection
- ASA status I-III, as defined by the American Society of Anesthesiologists
- Capable of giving informed consent

7.2 Exclusion Criteria

The presence of any one of the following exclusion criteria will lead to exclusion of the subject:

- Metastatic breast cancer
- No primary surgery (recurrence, reconstruction)
- Pre-operative chemotherapy or radiotherapy
- Significant immune impairment: auto-immune disease, HIV, other active cancer, age>85, ASA IV-V
- Concomitant regional anesthesia (epidural catheter, paravertebral blockade, wound infiltration with local anesthetics)
- Chronic opioids medication
- Any systemic immunosuppressive therapy (glucocorticoids, cytostatics, antibodies, drugs acting on immunophilins, interferon, TNF bindings proteins, mycophenolate)
- Known hypersensitivity or suspected allergy to propofol, soya or egg proteins

- Known hypersensitivity to volatile anesthetics (malignant hyperthermia)
- Women who are pregnant or breast feeding
- Inability to follow the procedures of the study, e.g. due to language problems, psychological disorders, dementia, etc. of the subject
- Participation in another study with investigational drug within the 30 days preceding and during the present study

Intraoperative radiotherapy is not an excluding criteria.

7.3 Subject Recruitment and Screening

All consecutive patients admitted for breast cancer surgery will be assessed for study eligibility by the anesthesiology staff. The attending anesthetist will inform patients about the study orally and in writing. Patients willing to participate will subsequently provide written informed consent. A pregnancy test will be performed.

Participation is on a strictly voluntary base. No compensation in any form will be granted to the subjects.

7.4 Early Withdrawal of Subjects

Patients will be informed about the possibility to retract their participation to the study at any time. Investigators may withdraw a patient prior to expected completion of the study for safety reasons (for instance as the result of an adverse event (AE) with unacceptable consequence or risk for the patient). In both cases, for patient safety, a final medical examination will be performed. Notification of the discontinuation will be clearly documented on the patient's case report form (CRF).

Since data collection and analysis will be performed following an intention-to-treat model, all consecutive patients will be analyzed according to the initial randomization group, regardless of the study drug administered. These patients will not be withdrawn from analysis.

7.4.1 Criteria for Early Withdrawal of Subjects

Initially included patients meeting unexpectedly exclusions criteria during the course of the study (such as: incidental findings of metastatic cancer, other surgical procedure as initially planned, reoperation within the first 5 postoperative days, patients receiving chemo- or radio- or any immunotherapy during the study course), or patients unable to follow study procedures (for instance, patients transferred to another hospital) will be considered as drop-outs and will not appear in the study analysis.

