
Statistical Methodology:
	
Primary analysis : the number of CTC in peripheral blood will be measured before and after exposition to general anesthesia using a linear mixed model with random effects matrix, which accounts for within-subject treatment factor (i.e. anesthesia regimen)
 
Secondary analyses: since most reports refer to CTC levels as a binary outcome (i.e. positive versus negative endpoints using a cut-off value of $\geq 5\text{CTC}/7.5\text{ ml blood}$), data transformation from continuous into a binary variable will be performed using the same cut-off value. This new data set will be analyzed using a logistic regression mixed model with random effects matrix.
 
All primary and secondary analyses will be performed following an intention-to-treat (IIT) model. This analysis will subsequently compared to a per-protocol analysis to ensure stability of results. Results will be reported as OR, 95% confidence intervals and their associated p-values. A p-value < 0.05 will be considered statistically significant

GCP Statement:
	
This study will be conducted in compliance with the protocol, the current version of the Declaration of Helsinki, and ICH-GCP as well as all national legal and regulatory requirements.

STUDY SCHEDULE

Study Periods	Screening	Treatment Period		Follow-up	
Visit	1	2	3	4	5
Postoperative day	-1	0a	0b	2	3
Medical history	x				
Physical Examination	x				
Vital signs		x	x	x	x
Concomitant therapy	x	x	x	x	x
In-/Exclusion Criteria	x				
Subject information and informed consent	x				
Pregnancy test	x				
Randomization		x			
Study medication (sevoflurane or propofol)			x		
1° variable: CTC level		x	x	x	x
2° variable A		x	x	x	x
2° variable B*			x		
2° variable C					
Perioperative data	x	x	x	x	x
Safety variables: AE			x	x	x

Visit 1: 24h before surgery

Visit 2 (0a): before induction of anesthesia

Visit 3 (0b): end of surgery, before extubation

Visit 4: 48h after surgery

Visit 5: 72h postoperative, before hospital discharge

Primary variable: assessment of circulating tumor cells in peripheral blood

Secondary variable A: assessment of natural killer (NK) cells (number and activity)

Secondary variable B: extracapsular tumor spread in axillary nodes

* Data will be collected after completion of the study

Perioperative data: demographics and confounding factors

TABLE OF CONTENTS

1.	LIST OF ABBREVIATIONS AND DEFINITIONS OF TERMS	8

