12.3 Planned Analyses

All primary and secondary analyses will be performed following an *intention-to-treat* (ITT) model. This analysis will be subsequently compared to a *per-protocol* analysis to assess the impact of patients who were not treated as randomized. Results will be reported as OR, 95% confidence intervals and their associated p-values. A p-value <0.05 will be considered statistically significant.

Data analyses will be performed after enrolment of the last patient and completion of the study. No interim analyses are planned.

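### Section 7.4.1 deletes randomised patients from the study analysis for mostly post-randomisation events, against the intention-to-treat rule in 12.3

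*Protocol*

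**What the plan says.** - **Protocol 12.3 (Planned Analyses):** "All primary and secondary analyses will be performed following an" intention-to-treat model. A per-protocol analysis is then compared with it "to assess the impact of patients who were not treated as randomized". The synopsis gives the purpose of that comparison as "to ensure stability of results".
- **Protocol 7.4 (Early Withdrawal of Subjects):** "all consecutive patients will be analyzed according to the initial randomization group, regardless of the study drug administered". It adds: "These patients will not be withdrawn from analysis".
- **Protocol 7.4.1:** two kinds of patient "will be considered as drop-outs and will not appear in the study analysis". The first kind unexpectedly meets exclusion criteria during the study. The examples are metastases found incidentally, an operation other than the one planned, "reoperation within the first 5 postoperative days", and chemo-, radio- or immunotherapy during the study. The second kind cannot follow study procedures, for instance because of transfer to another hospital. No analysis set is named.
- **Protocol 6.1:** randomisation is done "once the patient will be installed for induction of anesthesia".
- **Protocol 6.2:** CTC samples are taken before induction, at the end of surgery, and at 48 h and 72 h.
- **Protocol 7.4.2:** patients who unexpectedly meet exclusion criteria are still followed, with routine-care data recorded.
- **Protocol 12.4:** linear mixed models can use incomplete series without imputation.

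**The concern.** The protocol gives two incompatible instructions on who enters the primary analysis. An analyst could follow either and cite the protocol for it, and nothing stops the choice from being made after the data are seen.

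Under 7.4.1 the comparison is no longer between the groups as randomised. It is between those patients in each group who had none of the listed events. If removal is related to CTC level, and differently so in the two arms, the estimated difference is biased. Reoperation, later therapy and transfer belong to the postoperative course, which the anaesthetic could affect.

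The planned safeguard does not help. If 7.4.1 is followed, these patients are in neither the intention-to-treat nor the per-protocol set, so comparing the two sets cannot show what removing them did.

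**Working it through.** **1. Timing of the triggers.** Consent is on the day before surgery and randomisation is at induction on the day of surgery (6.1). Losses between the two are harmless. The listed triggers fall as follows:

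| Trigger in 7.4.1 | When it normally arises or is found |
|---|---|
| Incidental metastases | Found mostly at or after surgery, though probably present before randomisation |
| Operation other than planned | Mostly at surgery |
| Reoperation within 5 days | After surgery |
| Chemo-, radio- or immunotherapy during the study | Mostly after randomisation |
| Transfer to another hospital | After surgery |

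Reoperation and transfer are not named as exclusion criteria in 7.2. Most of the list is therefore not a correction of eligibility errors made at entry.

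**2. Window against sampling schedule.** The reoperation window is 5 × 24 h = 120 h and the last CTC sample is at 72 h. 120 − 72 = 48 h. A reoperation in those 48 h deletes a patient whose four primary values already exist.

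**3. Which set each section puts these patients in.**

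| Section | Intention-to-treat analysis | Per-protocol analysis |
|---|---|---|
| 12.3 | In | Meant to address patients not treated as randomised |
| 7.4, broad reading | In | Not addressed |
| 7.4, read as covering wrong-drug patients only | Not addressed | Not addressed |
| 7.4.1 | Out (no set is named) | Out |

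The conflict between 12.3 and 7.4.1 remains on either reading of 7.4.

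**4. Bias from removal.** In one arm let R be the mean of retained patients, e the fraction removed, and D the mean of removed minus retained patients. The full-arm mean is (1 − e)R + e(R + D) = R + eD. Hence

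full difference − retained difference = e1·D1 − e2·D2.

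The documents give neither e nor D, so the values below are assumed. D is in SD units, and the 0.3 effect size of 12.5 is read as SD units.

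| e1 | D1 | e2 | D2 | Shift (SD) | Share of 0.3 |
|---|---|---|---|---|---|
| 0.10 | 1 | 0.10 | 1 | 0.10 − 0.10 = 0 | 0% |
| 0.02 | 1 | 0.02 | 0 | 0.02 | 7% |
| 0.05 | 1 | 0.05 | 0 | 0.05 | 17% |
| 0.10 | 1 | 0.10 | 0 | 0.10 | 33% |
| 0.12 | 1 | 0.08 | 1 | 0.12 − 0.08 = 0.04 | 13% |
| 0.12 | 1 | 0.08 | 0 | 0.12 | 40% |
| 0.08 | 0 | 0.12 | 1 | −0.12 | −40% |

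Of 116 patients per arm, 2%, 5% and 10% are 2.3, 5.8 and 11.6 patients.

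**5. Sample size, for scale only.** The stated 116 per group can be reproduced by averaging three measurements with correlation 0.4. For a single measurement, n = 2·((1.960 + 0.842)/0.3)² = 174.4. The factor for three measurements is (1 + 2 × 0.4)/3 = 0.60, giving 174.4 × 0.60 = 104.7. Allowing for 10% dropout, 104.7/0.9 = 116.3. If the whole 10% allowance were used up by 7.4.1 removals, 116 × 0.9 = 104.4 per group would remain, with power of 79.9% in this model. No power loss is claimed.

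**The case against.** The strongest reply is that 7.4.1 is a specific, pre-listed exception, in effect a modified intention-to-treat rule under the wrong name. Section 7.4 speaks of the study drug received, and 12.3 describes the per-protocol comparison in terms of treatment received. On that view intention-to-treat here deals with wrong-drug patients and 7.4.1 deals with dropout. Blinding is also broad. Patients, surgeons, ward nurses, laboratory staff and the pathologist are blinded, the data collectors have no access to allocation until the final analysis, and the unblinded anaesthetist takes no part in data collection or analysis (8.6). Incidental metastases were probably present before randomisation, so removing those patients is a weaker problem. The bias figures are assumptions throughout.

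Parts of this stand:
- The narrow reading of 7.4 is possible.
- The bias argument applies mainly to reoperation, later therapy and transfer.
- The 40% case needs unequal removal averaging 10%, the whole dropout allowance, and a CTC difference in one arm only.
- Section 7.4.2 secures only routine-care data, so only values taken before the event are sure to be available.

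None of it reconciles 7.4.1 with 12.3. Section 12.3 covers all primary and secondary analyses and names no exception, and no passage calls 7.4.1 a modified set. Blinding makes arm-selective removal less likely, but it does not settle which rule applies. It also does not prevent an effect of the anaesthetic on the postoperative course, or restore deleted values. A SAP could define the sets in detail, but here the protocol itself gives two contrary rules.

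**Conclusion.** The concern holds and must be fixed: 7.4.1 is wrong as written. The conclusion rests on the texts of 7.4.1 and 12.3 and on randomisation at induction, not on the illustrative bias figures. The size and direction of bias are unknown. It is zero if removed patients differ from retained ones equally in both arms and removal rates are equal. Under the assumed cases it lies between −0.12 and +0.12 SD, up to 40% of the planned effect; this is not an upper limit. The examination of missing data in 12.4 covers dropouts but would not bring back values that 7.4.1 takes out of the analysis.

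**What to change.** 1. **7.4.1:** replace the removal clause with: *Randomised patients meeting these criteria remain in the intention-to-treat set in their randomised group and contribute every CTC and NK value obtained; they are excluded from the per-protocol set only.*
2. **12.3:** add: *The per-protocol set excludes patients not treated as randomised and patients meeting a criterion in 7.4.1.*
3. **12.4:** state that the examination of missingness includes the 7.4.1 patients, and that the mixed model without imputation is valid only if data are missing at random.

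In the same edit, reconcile the radiotherapy trigger in 7.4.1 with 7.2 and 8.4, which say that intraoperative radiotherapy is not a reason for exclusion. Otherwise the new per-protocol wording could be read as dropping those patients.

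The cost is wording only. The sample size stays at 232 and no visit or sample is added. The downside is that later CTC and NK samples may be missing for some of these patients, and the gaps may be informative after reoperation or transfer. Keeping the observed values is still better than deleting them.

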7.4.2 Data Collection and Follow-up for Withdrawn Subjects

Patients withdrawn because of an adverse event (AE) or patients unexpectedly meeting exclusion criteria will be followed during the study course. Data available through routine care will be recorded in the CRF unless the patient specifically refuses the investigators to access the medical record.

7.5 Early Termination of Study

The Sponsor-Investigator may terminate the study prematurely according to certain circumstances:

- ethical concerns,
- insufficient patient recruitment,
- when the safety or benefit of the subjects is doubtful or at risk, respectively,
- alterations in accepted clinical practice that make the continuation of a clinical trial unwise,
- reaching a positive or negative statistical end point earlier than anticipated.

